5.6.7 Other Safety Analyses

LVEF

LVEF and change from baseline to lowest postbaseline value will be summarized by visit. Change from baseline to lowest postbaseline category (no reduction, >0 - \leq 10%, >10 - \leq 15%, >15%), change from baseline to lowest postbaseline value <50% (frequency and percentage) will be presented. Subjects will be included in the change summary only if they had both a baseline value and at least one postbaseline value.

A table summarizing the shift from baseline to the worst postbaseline LVEF category will be presented. LVEF values will be categorized as:

- Hyperdynamic/Normal: LVEF greater than 70%, or LVEF 50% to 70% (midpoint 60%)
- Mild dysfunction: LVEF 40% to 49% (midpoint 45%)
- Moderate dysfunction: LVEF 30% to 39% (midpoint 35%)
- Severe dysfunction: LVEF less than 30%.

Subject data listings will be provided.

ECOG PS

The number (percentage) of subjects for each category of ECOG PS will be summarized by shift from baseline to the highest postbaseline scale of ECOG PS.

Subject data listings will be provided.

5.7 Other Analyses

A separate pre-specified HRQoL analysis following FDA and EMEA PRO Guidelines will be performed and detailed in a separate SAP and HRQoL report. Scoring of EQ-5D-5L and derivation of utility for health economic analysis will also be accomplished in a separate analysis and described in a separate HRQoL report.

5.8 Exploratory Analyses

Exploratory analyses may be conducted as appropriate. Any performed exploratory analyses will be appropriately titled and labeled as exploratory and will be clearly distinguished from planned analyses when results are reported in the Clinical Study Report.

6 INTERIM ANALYSES

As of Amendment 03, Expansion part may be further expanded up to approximately 94 evaluable subjects. For this expansion decision, 2 interim analyses will take place when 20 (6 subjects for DLT evaluation part plus 14 subjects for Expansion part) and 56 subjects (6 subjects for DLT evaluation part plus 50 subjects for Expansion part) have sufficient follow-up to be evaluated for response. The decision to expand enrollment will be based on the results of 2 interim analyses, which will spend $\beta = 0.012$ and $\beta = 0.024$ at the first and second interim analyses, respectively. The decision to expand enrollment will be assessed by mRECIST based on investigator review.

Based on an assumption of H_0 : 25% ORR and H_1 : 45% ORR, the 100-subject design with two futility analyses has approximately 96% statistical power at 2-sided $\alpha = 0.02$ (that corresponds to 1-sided $\alpha = 0.01$). At the first interim analysis ($N = 20$), if there are more than 5 responses, then approximately 36 additional subjects will be enrolled. At the second interim analysis ($N = 56$), if there are more than 16 responses, approximately 44 additional subjects will be enrolled. If there are 5 or fewer responses at the first interim analysis ($N=20$) or 16 or fewer responses at the second interim analysis ($N=56$), the sponsor may decide whether to expand enrollment based on clinical outcome (eg, DOR).

The boundaries for the decision to expand enrollment in Expansion part are presented in [Table 2](#).

7 CHANGES IN THE PLANNED ANALYSES

There were no major changes and deletions in the planned analyses in the protocol. Based on communications with the FDA toward the Type B meeting (that was scheduled on 10 Oct 2019), statistical analysis plan for the 1L HCC subjects to support AA applications were added, in addition to the planned analyses in the protocol on all HCC subjects including the subjects with prior anticancer medication.

8 DEFINITIONS AND CONVENTIONS FOR DATA HANDLING

The data will be handled as follows. The sponsor will determine how to handle all data prior to data base lock.

8.1 General Data Handling

Definition of Baseline data

Baseline is defined as the last non-missing value observed on or prior to the first dose of study treatment for a given parameter.

Definition of Change from Baseline, Percent Change from Baseline

Change from baseline is defined as post-baseline value minus baseline value.

Percent change from baseline is defined as follows:

$$\% \text{ Change from baseline} = (\text{Change from baseline} / \text{Baseline}) * 100\%$$

For any Baseline value of 0, the subject's corresponding percent change from baseline will not be included in the summary statistics table.

Handling of data not within specified periods or within the follow-up period

All the safety parameters will be used for summary statistic tabulation, except when it is irrelevant such as the situation where tests scheduled to be conducted before administration of the investigational drug were actually conducted after its administration.

8.2 Efficacy Data Handling

Handling of missing data

For the analysis of tumor response related endpoints (ORR, DCR, and CBR), subjects with missing response status (subjects whose baseline or post-baseline tumor assessment is missing) will be coded as non-responders on Efficacy Analysis Set.

Censoring rules for primary PFS analysis

The following table provides the censoring rules for primary PFS analysis.

No.	Situation	Date of Event (Progression/Death) or Censoring	Outcome
1	No baseline tumor assessments	Date of first dose	Censored
2	Progression documented between scheduled visits	Date of first radiologic PD assessment	Event
3	No progression at the time of data cut-off	Date of last adequate radiologic assessment before or on date of data cut-off	Censored
4	New anticancer treatment started	Date of last adequate radiologic assessment prior to or on date of new anticancer treatment	Censored
5	Death before first PD assessment	Date of death	Event
6	Death between adequate assessment visits*	Date of death	Event
7	Death or progression after more than one missed visit/tumor assessment**	Date of last adequate radiologic assessment before missed tumor assessments	Censored

CR = complete response, PD = progressive disease, PR = partial response, SD = stable disease,

* Adequate tumor assessment is radiologic assessment of CR, PR, SD, non-CR/non-PD, or PD at regular interval as defined in the protocol.

** More than one missed visit/adequate tumor assessment is defined as having either one of the following two durations being longer than 12 weeks + 2 weeks (ie, the date of death or PD – the date of last adequate tumor assessment >97 days) for subjects on the every 6 week tumor assessment schedule in the first 8 cycles of treatment and 18 weeks + 2 weeks (ie, the date of death or PD – the date of last adequate tumor assessment >139 days) for subjects on the every 9 week tumor assessment schedule after Cycle 8 in this study.

The priority of the censoring rules is as follows:

1. If the subject had PD or death, the following sequence will be applied:
 - If a subject did not have a baseline tumor assessment (No. 1), the subject will be censored on the date of first dose. However, if the subject died within 97 days (14 weeks -1 day) after first dose and did not receive a new anticancer treatment, it will be counted as PFS event at the date of death.
 - If a subject had new anticancer treatment before PD or death (No. 4), the subject will be censored on the date of the last adequate tumor assessment prior to or on the date of new anticancer treatment.
 - If a subject missed two or more tumor assessments before PD or death (No. 7), the subject will be censored on the date of the last adequate tumor assessment before PD or death. Note that if a subject is censored by both this criterion and the anticancer treatment criterion, the earliest censoring date will be used.

- Otherwise, if a subject had an event (No. 2, No. 5, or No. 6), the earliest event date will be used.
2. If a subject did not have PD or death, the censoring date will be the earliest censoring date if the subject met multiple censoring criteria (No. 1, No. 3, No. 4, or No. 7).

Censoring rules for primary DOR and TTP analysis

The censoring rules for DOR and TTP will be the same as those for primary PFS analysis, except that:

No baseline tumor assessments (No. 1) will not apply for DOR, Death before first PD assessment (No. 5) and death between adequate assessment visits (No. 6) will not apply to TTP. Death without new anticancer treatment will be censored at the last adequate tumor assessment for TTP.

Censoring rules for supplementary analysis

The censoring rules for the supplementary analysis described in [Section 5.4.4](#) will follow the censoring rule for the primary PFS analysis specified above with the exception that the following rule will be applied instead of the primary rule for situation No. 7.

No.	Situation	Date of Event (Progression/Death) or Censoring	Outcome
7	Death or progression immediately after more than one missed visit/tumor assessment**	Date of last adequate radiologic assessment before missed tumor assessments	Censored

- If a subject missed two or more tumor assessments **right** before PD or death (No. 7), the subject will be censored on the date of the last adequate tumor assessment before PD or death. Note that if a subject is censored by both this criterion and the anticancer treatment criterion, the earliest censoring date will be used.

For example, following this rule, supplementary analysis will be handled as below for each scenario:

- PR, PR, two missing scans, PR, PR, then DOR is censored at the fourth PR date (instead of the censoring at the second PR based on the primary analysis)
 - PR, PR, two missing scans, PD, then DOR is censored at the second PR date (same as the primary analysis)
 - PR, PR, two missing scans, PR, PD, then DOR has an event at the PD date (instead of the censoring at the second PR based on the primary analysis)
- etc.

Censoring rules for OS

No.	Situation	Date of Event (Death) or Censoring	Outcome
1	Death before or on data cut-off	Date of death	Death
2	Death after data cut-off	Date of data cut-off	Censor
3	Alive at data cut-off	Date of data cut-off	Censor
4	Lost to follow-up or withdrawal of consent before data cut-off	Date last known to be alive	Censor

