3.2 Overall Study Design and Plan

This is an open-label Phase 1b study. This study will evaluate the tolerability and safety of lenvatinib in combination with pembrolizumab in subjects with HCC.

This study will begin with lenvatinib 12 mg (body weight [BW] ≥ 60 kg) or 8 mg (BW < 60 kg) /day orally and pembrolizumab 200 mg (every 3 weeks [Q3W], intravenous [IV]) in subjects with HCC. Tolerability of this dose level will be evaluated by dose limiting toxicities (DLTs) during the first cycle (21-day treatment cycle).

In this dose level, 3 subjects will be enrolled first. If 0 or 1 of 3 subjects in a given dose level cohort experiences a DLT, then 3 more subjects will be enrolled into that dose level. If 0 or 1 of 6 subjects in a given dose level cohort experiences a DLT, the dose level will be considered tolerable. Additional 4 subjects can be enrolled without DLT evaluation if further

safety information is considered necessary based on the discussions between the sponsor and investigators.

Enrollment will be interrupted if 2 or more DLTs are observed in this dose level, and after sponsor and investigators' review, enrollment may continue for up to 6 subjects based on the nature and severity of the DLTs. Once 6 subjects are enrolled, after sponsor and investigators' review regarding the nature and severity of the DLTs, an additional 4 subjects (10 subjects in total for DLT evaluation) will be enrolled, and that dose level will be considered to be tolerable if DLT is observed in 3 or less of the 10 subjects in total. An independent medical advisor as third party may be consulted for the review as needed.

In this dose level, at least 3 subjects treated with lenvatinib 12 mg once daily (QD) and pembrolizumab 200 mg Q3W IV (BW \geq 60 kg) need to be included in the 6 subjects for DLT evaluation. (In case of the 10 subjects for DLT evaluation, at least 5 subjects (BW \geq 60 kg) treated with lenvatinib 12 mg QD and pembrolizumab 200 mg Q3W IV need to be included.)

Cohort of reduction to lower dose level (lenvatinib) or study discontinuation will be considered, if this dose level (12 mg [BW \geq 60 kg] or 8 mg [BW <60 kg] lenvatinib plus 200 mg pembrolizumab) is not tolerable, upon discussions between the sponsor and investigators, and the protocol will be amended as necessary. An independent medical advisor as third party may be consulted for the consideration as needed.

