A waterfall plot will illustrate the maximum post-baseline percent changes from baseline in the sum of the diameters of target lesions (ie, maximum tumor shrinkage). The number (percentage) of subjects with maximum tumor shrinkage $>0\%$, $\geq 50\%$, and $\geq 75\%$ will be summarized, using the number of subjects with both baseline and postbaseline sum of diameters of target lesions as the denominator. A spider plot will illustrate the percent changes from baseline in the sum of the diameters of target lesions over time. Swimmers' plots showing duration of treatment, the initial response timepoint, disease progression timepoint, death timepoint, and treatment ongoing status will be provided.

Data cutoff for the primary analysis will be done after all subjects in the Expansion part finish at least Cycle 8 assessment and have a tumor assessment of at least Week 24, or discontinue if before Cycle 8. Based on communications with the FDA, this primary analysis will be conducted with the data cutoff date of 31 Oct 2019.

Subject data listings will be provided.

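### Neither missed-assessment limit in Section 8.2 fits a gap that starts at the Week 18 scan, and the footnote does not say which schedule governs

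*SAP*

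**What the plan says.** The censoring table in SAP Section 8.2 has a rule No. 7 for death or progression after more than one missed assessment. The outcome is censored at the last adequate assessment before the missed ones. The priority list that follows states the rule as a count of scans: "If a subject missed two or more tumor assessments before PD or death (No. 7"). The worked examples for the supplementary analysis count missing scans too.

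The double-asterisk footnote converts the count into days:

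- the 6-weekly limit is 12 + 2 weeks and holds "for subjects on the every 6 week tumor assessment schedule in the first 8 cycles of treatment"; as a day rule for the gap up to PD or death it reads "the date of last adequate tumor assessment >97 days";
- the 9-weekly limit is 18 + 2 weeks and holds "for subjects on the every 9 week tumor assessment schedule after Cycle 8 in this study"; as a day rule for the same gap it reads "the date of last adequate tumor assessment >139 days".

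Section 8.2 carries these rules over to DOR and TTP, with exceptions that do not touch No. 7. The supplementary analysis rewords No. 7 but keeps the same footnote mark.

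**The concern.** The footnote has one limit for each schedule and none for a gap with one interval of each kind. It also does not say whether a subject's schedule is read at the last adequate scan or at the date of PD or death. Two programmers could follow the text and classify the same subject differently.

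DOR by independent review is a primary efficacy endpoint (Sections 5.1.1 and 5.4.1). Censoring a real progression after one missed scan removes an event and tends to lengthen DOR and PFS. Counting an event that the rule meant to censor works the other way. Section 5.4.1 also reports the number of responders with DOR of at least 6 months, and a single reclassification can change that count.

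**Working it through.** **Inputs.** The treatment cycle is 21 days (Section 3.2). Scans are 6-weekly in the first 8 cycles and 9-weekly afterwards (Section 8.2 footnote). The data-cutoff condition in Section 5.4.1 pairs Cycle 8 with Week 24: "finish at least Cycle 8 assessment and have a tumor assessment of at least Week 24". Section 8.2 itself equates 97 days with 14 weeks less one day.

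**Calendar.** 8 × 21 = 168 days = 24 weeks. Scans therefore fall at Weeks 6, 12, 18 and 24, then 33, 42, 51 and so on. This is inferred; the protocol's scan windows are not shown.

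**The SAP's own limits.** Limit = (sum of the next two scan intervals + 2 weeks) × 7 − 1 day.

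- 6-weekly: (6 + 6 + 2) × 7 − 1 = 97, as stated.
- 9-weekly: (9 + 9 + 2) × 7 − 1 = 139, as stated.

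**The same formula around the change of schedule.**

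| Last adequate scan | Next two scans | Limit by the SAP's convention | If >97 is applied | If >139 is applied |
|---|---|---|---|---|
| Week 12 | 18, 24 | 97 | right | wrongly counts gaps of 98–139 days |
| Week 18 | 24, 33 | (6 + 9 + 2) × 7 − 1 = 118 | wrongly censors 98–118 days | wrongly counts 119–139 days |
| Week 24 | 33, 42 | 139 | wrongly censors 98–139 days | right |

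Only Week 18 needs a value that the SAP does not contain. Either stated limit is wrong there over a band of 21 days.

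**Examples from Week 18.**

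- Week 24 missed, PD at the scheduled Week 33 scan: (33 − 18) × 7 = 105 days, one missed scan. Under >97 it is censored at Week 18.
- Weeks 24 and 33 missed, death or off-schedule PD at Week 36: (36 − 18) × 7 = 126 days, two missed scans. Under >139 it counts as an event.
- Weeks 24 and 33 missed, PD at the scheduled Week 42 scan: (42 − 18) × 7 = 168 days. Both limits censor it, correctly.

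**Effect of the unstated anchor.**

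- Schedule read at the last scan, with Week 24 treated as 9-weekly: only the Week 18 error remains (98–118 days wrongly censored).
- Schedule read at the event: the Week 18 error becomes the other one (119–139 days wrongly counted). Gaps of 98–139 days from Week 12, all of which end after Week 24, also escape. For example, with Weeks 18 and 24 missed and an off-schedule PD at Week 30, (30 − 12) × 7 = 126 days, which is under 139.

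**What one subject can change.** Take first response at Week 6, later confirmed, last adequate scan at Week 18, Week 24 missed and PD at Week 33. DOR is (33 − 6) × 7 + 1 = 190 days with an event. If censored at Week 18, it is (18 − 6) × 7 + 1 = 85 days without one. Six months at 365.25/12 days per month is 182.6 days, so the subject also drops out of the count with DOR of at least 6 months.

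**Weight of one subject.** This is an assumption, since the responder count is unknown. Taking the SAP's two design rates in the first 80 subjects, 25% gives 20 responders and 45% gives 36. One subject is then 1/20 = 5.0% or 1/36 = 2.8% of the DOR analysis.

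**The case against.** The strongest reply is that the footnote defines more than one missed assessment by these durations. They would then be the operative rule, and a fixed window is a legitimate simplification. That would settle the matter if the section did not also state the rule as a count of two or more scans and illustrate it with counted scans. At Week 18 the two statements disagree.

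A second reply is that the calendar is inferred and that Section 9 leaves programming derivations to separate documents, where the anchor may be fixed. The dependence on the calendar is real. A separate specification could settle the anchor, but neither stated limit would fit Week 18 whichever anchor it chose.

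A reader might infer that the limits fail for every gap near the change of schedule. The SAP does not support that. From Week 24 to Week 42 both intervals are 9-weekly. The gap of 126 days is under 139, so PD after one missed scan counts correctly, unless the Week 24 scan is treated as 6-weekly although the next scan is due 9 weeks later. The Week 12 to Week 30 case fails only if the schedule is read at the event, and it needs an off-schedule PD or a death. PD at the scheduled Week 33 scan is (33 − 12) × 7 = 147 days from Week 12 and is censored under either limit.

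**Conclusion.** The point holds in a narrow form. For a last adequate scan at Week 18 neither stated limit matches the SAP's own convention, and the footnote leaves the governing schedule open. For gaps wholly within one schedule both limits are correct. The supplementary analysis does not cure the problem, because it uses the same definition of a missed assessment.

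The effect is probably small. For PD found at a scheduled scan, the error needs a last adequate scan at Week 18, a missed Week 24 scan and first PD at about Week 33. The opposite error touches only deaths and off-schedule progressions. A reader might infer material bias in the primary DOR result; the SAP gives no missed-scan rate, so the number of affected subjects cannot be estimated and may be zero. ORR is not affected; DOR, PFS and TTP are. The conclusion assumes that scans run on calendar weeks from first dose, with Week 24 the last 6-weekly scan.

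**What to change.** Replace the two limits in the footnote with one rule anchored at the last adequate scan: more than 97 days if that scan is at or before Week 12, more than 118 days if at Week 18, more than 139 days if at or after Week 24. Equivalently, the limit is the date of the second scheduled scan after the last adequate one, plus 2 weeks, minus 1 day. State that it applies to PFS, DOR and TTP and to the supplementary analysis, and check the calendar against the protocol's assessment schedule and windows.

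The cost is one sentence in Section 8.2 and a small change to the derivation program, to be settled before database lock.

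### SAP section 8.2: the priority bullet and footnote for censoring rule No. 7 contradict its own table row and the worked examples, so primary DOR (and PFS, TTP) has more than one derivation

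*SAP*

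**What the plan says.** All of the texts below are in SAP section 8.2.

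- **Primary table, row 7.** Situation: "Death or progression after more than one missed visit/tumor assessment". Date: "Date of last adequate radiologic assessment before missed tumor assessments". The outcome is censored.
- **Footnote \*\***, attached to row 7. It is the only numerical definition of more than one missed assessment. On the 6-weekly schedule the test is "the date of death or PD – the date of last adequate tumor assessment >97 days". On the 9-weekly schedule the same interval is compared with 139 days.
- **Priority list, item 1, primary bullet.** A subject who missed two or more assessments "before PD or death (No. 7), the subject will be censored on the date of the last adequate tumor assessment before PD or death".
- **Priority list, item 2**, for subjects with neither PD nor death. The earliest censoring date is used "if the subject met multiple censoring criteria (No. 1, No. 3, No. 4, or No. 7".
- **Supplementary table, row 7.** Situation: "Death or progression immediately after more than one missed visit/tumor assessment". It carries the same ** marker, and its bullet uses the same date wording as the primary bullet.
- **Worked examples.** In example 1 (PR, PR, two missing, PR, PR) the supplementary rule applies, and "then DOR is censored at the fourth PR date (instead of the censoring at the second PR based on the primary analysis". In example 2 (PR, PR, two missing, PD) both analyses censor at the second PR. In example 3 (PR, PR, two missing, PR, PD) the supplementary analysis has an event at PD, while the primary analysis censors at the second PR.
- **Other endpoints.** "The censoring rules for DOR and TTP will be the same as those for primary PFS analysis", with exceptions that do not touch No. 7.

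**The concern.** Row 7 and the examples show one intended primary rule: any run of two or more missed scans censors the subject at the last adequate scan before that run. Two operative texts do something else.

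The primary bullet fires on any such run before PD or death but takes the date from the scan just before PD or death. If adequate scans follow the gap, it credits the response time up to the last of them and then discards the observed progression.

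The footnote fires only when the gap ends in PD or death. That is the supplementary rule. Because the same footnote serves both tables, the words that separate the two rules (after, and immediately after) get the same trigger. For event-free subjects, priority item 2 and example 1 invoke No. 7, but row 7 and the footnote both require PD or death, so no gap is defined.

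At stake is DOR by IIR in the first 80 first-line subjects, a primary efficacy analysis (sections 5.1.1 and 5.4.1), with its Kaplan-Meier estimates and the percentage of responders with DOR of at least 6 months. The supplementary analysis in section 5.4.4 is also at stake, since it is meant to test this rule.

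**Working it through.** **The SAP's day limits.** 12 + 2 weeks: 7 × 14 − 1 = 97 days. 18 + 2 weeks: 7 × 20 − 1 = 139 days. Both reproduce, so the limits are not the problem.

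**Inputs.** DOR = end date − first PR date + 1 (section 5.4.1). PFS and TTP = end date − first dose date + 1 (section 5.4.2). Scans are 6-weekly in the first 8 cycles and 9-weekly afterwards (section 8.2, footnote). A cycle is 21 days (section 3.2), so 8 cycles end at Week 24.

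**Assumption.** The full scan calendar is not in the SAP. I take scans at Weeks 6, 12, 18, 24, 33 and 42 after first dose, with Weeks 18 and 24 missed.

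**Example 3: PR Week 6, PR Week 12, two missed, PR Week 33, PD Week 42**

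| Text followed | End date | DOR (days) | PFS and TTP (days) | Status |
|---|---|---|---|---|
| Row 7 and examples | Week 12 | (12 − 6) × 7 + 1 = 43 | 12 × 7 + 1 = 85 | Censored |
| Primary bullet | Week 33 | (33 − 6) × 7 + 1 = 190 | 33 × 7 + 1 = 232 | Censored |
| Footnote ** | Week 42 | (42 − 6) × 7 + 1 = 253 | 42 × 7 + 1 = 295 | Event |

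The footnote row follows because PD minus the last adequate scan is (42 − 33) × 7 = 63 days, below both limits, so No. 7 does not fire. The real gap, Week 12 to Week 33, is 147 days, above both limits, but the footnote never measures it.

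The three-way split does not depend on the calendar. DOR is 43, 169 or 211 days if all scans are 6-weekly, and 64, 253 or 316 days if all are 9-weekly.

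**Example 1: ongoing response.** There is no PD or death, so the bullet does not apply and the footnote interval does not exist. The example gives 43 days. Without a usable trigger, the subject is censored at the last scan, 253 days.

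**Example 2: gap running directly into PD.** PD at Week 33 is 147 days after the last adequate scan. Every text gives censoring at Week 12, 43 days. The conflict therefore arises only when an adequate scan follows the gap.

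**Effect on the percentage with DOR of at least 6 months.** Six months is 6 × 365.25/12 = 182.6 days. In examples 1 and 3 the choice of text crosses that line. Using the planning rates in section 4 only as a range, 45% of 80 is 36 responders and 25% of 80 is 20. One affected responder moves the percentage by 1/36 = 2.8 points to 1/20 = 5.0 points.

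**Which limit applies across the schedule change (secondary).** On the same calendar:

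- Last scan Week 18, only Week 24 missed, PD Week 33: (33 − 18) × 7 = 105 days. The 97-day limit flags this with one scan missed.
- Last scan Week 12, Weeks 18 and 24 missed, death Week 30: (30 − 12) × 7 = 126 days. The 139-day limit does not flag this with two scans missed.

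**How often the texts would differ.** This can only be illustrated. The simulation assumed first response at Week 6, 12 or 18 (45/40/15%), exponential DOR with median 9 or 18 months, independent misses, and follow-up uniform over 6 to 18 months. At 5 to 10% missed scans, the footnote and row 7 differ in about 0.3 to 2% of responders, or 0.1 to 0.7 of 36. If the 97-day limit is applied to gaps spanning the schedule change, this rises to about 3 to 9%, or 1.1 to 3.2 of 36.

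**The case against.** The strongest reply is that the SAP already states the intended result. Three examples each say what the primary analysis does, and row 7's date agrees with all of them. The bullets sit under a heading about priority, so they could be read as setting only the order of application, and section 9 leaves derivation rules to separate documents. On this view the point is a wording clean-up. DOR is summarised descriptively with no planned comparison (section 5.3.3), and at ordinary miss rates fewer than one responder may be affected.

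Much of this stands. The intent is clear, and the fix follows it. The footnote conflicts more directly with examples 1 and 3 than with row 7, since it defines row 7's own term. Its mention of two durations does not help, because both formulas given end at PD or death. The claim that the supplementary analysis repeats the primary is strict only for subjects with PD or death. For event-free subjects the trigger is undefined rather than identical, and example 1 shows that a difference was intended.

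The reply fails on one point: the examples supply no computable trigger, and the only one in the SAP contradicts them. Two programmers could each follow SAP text and produce different primary DOR data. Independent misses are also an assumption, and the expected count depends on the unresolved limit at the schedule change.

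**Conclusion.** The concern holds. Section 8.2 gives one primary rule in row 7 and the examples, and contradicts it in the primary bullet (date) and in the footnote (trigger). For a subject like example 3 the choice decides between 43 days censored, 190 days censored and a 253-day event. The day counts rest on an assumed calendar, but the disagreement does not. If the footnote is followed, the supplementary analysis cannot differ from the primary for subjects with PD or death.

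The texts agree when the gap runs directly into PD or death, and ORR is untouched. The number of subjects affected is unknown and probably small; the simulated frequencies are illustrative and the conclusion does not rest on them. It should be fixed before database lock because it concerns a primary endpoint in a regulatory submission and costs almost nothing to correct.

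**What to change.** Amend section 8.2 before database lock so that the text matches row 7 and the examples:

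1. In footnote **, define the primary gap as the time between any two successive adequate assessments, or from the last adequate assessment to PD or death. Reserve the gap ending directly in PD or death for the supplementary rule, with its own footnote.
2. In the primary priority bullet, set the censoring date to the last adequate assessment preceding the run of missed ones.
3. Extend row 7 to subjects without PD or death, in line with priority item 2 and example 1.
4. State whether 97 or 139 days applies to a gap spanning the change from 6-weekly to 9-weekly scans, derived from the protocol's scan schedule.
5. Report the number of responders whose DOR date or status differs between the primary and supplementary rules.

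The cost is SAP wording and a short check of the derivation against the three examples. Both analyses are already planned for the first 80 subjects, so the only new output is one count.
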